6.18. Safety Analyses

The planned safety analyses are consistent with compound-level standards, which are based on various sources, including company standards, internal and external subject matter experts, and cross-industry initiatives (e.g., white papers produced by a PhUSE Computational Science Working Group [a collaboration with FDA and PhUSE], published in the PhUSE Deliverables Catalog). Descriptions of the safety analyses are provided in this SAP; however, some details are in compound-level safety standards.

The detail of analysis and corresponding period and population is defined in Section [6.1.1](#) and [Table JAHV.6.10](#).

Table JAHV.6.10. Summary of Safety Analysis Population, Period, Duration of Exposure and Baseline

Population for safety analysis (Section 6.1.1)	General Safety Population	DBW Safety Population	
		Baricitinib	Placebo
Treatment period	OLLI period and Safety/PK assessment period	DBW period	
Duration of study drug exposure	date of last dose of baricitinib in safety/PK assessment or OLLI period – date of first dose of baricitinib in Safety/PK assessment or OLLI period + 1	date of last dose of treatment in DBW period – date of randomization in DBW period + 1	
Baseline for LLT used in defining treatment-emergence and change from baseline analysis	Baseline period: The start of screening and ends prior to the time of first dose of bari administration. (For labs, vital signs and growth: baseline will be all scheduled and unscheduled measurements recorded during baseline period.)		
Postbaseline for LLT used in defining treatment-emergence and change from baseline analysis	
The event start time (onset time) is on or after first dose of baricitinib in Safety/PK assessment period or OLLI period, before time of randomization in DBW period (include up to 30 days off-drug follow-up time if patient did not enter DBW period).
 
For treatment-emergent abnormal labs, vital signs and shift summaries in labs, all scheduled and unscheduled measurements will be included.
 
For change from baseline labs, vital signs and growth, only scheduled visits will be included. The early termination visits (ETV) are considered scheduled visits.
	
The event start time (onset time) is on or after time of randomization in DBW period, up to 30 days off-drug follow-up time.
 
For treatment-emergent abnormal labs, vital signs and shift summaries in labs, all scheduled and unscheduled measurements will be included.
 
For change from baseline labs, vital signs and growth, only scheduled visits will be included. The early termination visits (ETV) are considered scheduled visits.
	

Abbreviations: Bari = baricitinib; DBW = double-blind withdrawal; OLLI = open-label lead-in; JIA = juvenile idiopathic arthritis; LLT = Lowest Level Term; PK = pharmacokinetics.

Safety topics that will be addressed include the following: AEs, clinical laboratory evaluations, vital signs and physical characteristics, safety in special groups and circumstances, including adverse events of special interest (AESI) (see Section 6.18.5).

Unless otherwise specified, by-visit summaries will include planned on-treatment visits. For tables that summarize events (such as AEs, categorical lab abnormalities, shift to maximum value), post-last dose follow-up data will be included. For deaths and malignancies, all available follow-up data up to the end of the study will be included. Listings will include all safety data.

The following statistical methods will be used for safety analysis during the DBW period with the DBW safety population unless otherwise noted:

- The Fisher exact test will be used for treatment comparisons of proportions, and odds ratios with corresponding 95% confidence intervals will be provided.
- Treatment differences in mean change for continuous measurements will be assessed using an ANCOVA model fitting “baseline” as a covariate. Type 3 sums of squares will be used.

Though p-values will be provided for many of the safety analyses, they should not be overinterpreted. They correspond to data-driven hypotheses and are only useful as a flagging mechanism.

Statistical significance is designated at 2-sided p-values (rounding up to 3 decimal places) ≤ 0.05 for tests of treatment differences. However, p-values should not be overinterpreted.

Exposure-adjusted incidence rate (EAIR) will be provided for selected topics. The EAIR is evaluating the incidence of a first event per 100 patient-years at risk (PYR). Exposure will be calculated based on the analysis period defined as the treatment period plus up to 30 days off-drug follow-up time. Exposure time for a patient with an event will be counted up to the time of the start of event. Exposure time for a patient without an event will be censored at the end of the analysis period. For each EAIR provided, a Poisson distribution 95% CI may be calculated. Treatment group comparisons, when provided, will be provided based on the incidence rate difference (IRD) together with its 95% CI.

Not all displays described in this SAP will necessarily be included in the CSR. Any display described in this SAP and not provided in the CSR would be available upon request. Not all displays will necessarily be created as a “static” display. Some may be incorporated into interactive display tools instead of or in addition to a static display. Any display created interactively will be included in the CSR if deemed relevant to the discussion.

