10.3.4. Safety Analyses

Safety variables will be summarized, which include the following but are not limited to:

- Exposure to investigational product
- AEs
- SAEs
- Permanent discontinuation of investigational product
- Temporary interruption of investigation product

- AEs leading to discontinuation
- AEs of special interest
- Laboratory analytes (hematology and chemistry [including ALT and AST], neutrophil counts, and immunological measurements)
- Vital signs

Primary safety analyses will summarize baricitinib and placebo treatment groups for DBW population in DBW period. The Fisher exact test will be used for the AEs, discontinuation, and other categorical safety data for between-treatment-group comparisons in the DBW period. Continuous vital signs, body weight, and other continuous safety variables, including laboratory variables, will be analyzed using ANCOVA with treatment and baseline value in the model.

Summaries of safety data will be presented for baricitinib in OLLI period using OLLI population and throughout the study using general safety population unless otherwise stated.

Sensitivity analysis may be performed when there are patients who did not take investigational product after randomization in DBW. Pharmacokinetic analysis will be conducted using all evaluable PK data in safety/PK population. Further details will be described in the SAP.

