6.1.1. Analysis Populations

For purposes of analysis, the following populations are defined based on the different treatment period as shown in [Table JAHV.6.1](#).

Table JAHV.6.1. Analysis Populations

	Population	Description
	Entered population	All participants who sign informed consent.
Efficacy Analysis population	Safety/PK population	All patients who received at least 1 dose of investigational product in the Safety/PK assessment period.
	OLLI population	All participants who take at least 1 age-based final dose, as confirmed by PK assessments of investigational product, in the OLLI period, other than the Safety/PK population.
	OLLI population 2	All patients who received at least 1 dose of investigational product in the OLLI period.
	Safety/PK and OLLI population	All enrolled patients who were initially assigned to the open-label investigational product in Safety/PK assessment period and OLLI period, following intent-to-treat (ITT) principles.
	DBW population	All randomized patients in the DBW period following intent-to-treat (ITT) principles.

	Population	Description
Safety Analysis population	DBW safety population	All randomized patients in the DBW period who receive at least 1 dose of investigational product.
	General safety population	All patients who received at least 1 dose of investigational product, which is baricitinib.

Abbreviations: DBW = doubleblind withdrawal; OLLI = open-label lead-in; PK = pharmacokinetic.

Efficacy analyses will be conducted by treatment periods with the corresponding analysis population, where the primary efficacy analysis will focus on the DBW period with the DBW population. Safety analyses will be performed by treatment periods with the corresponding safety population.

The patients who participate in the Safety/PK period and participate in the OLLI period with the age-based final dose will be eligible to participate in the DBW period if the patient is a PedACR30 responder at the end of the OLLI period. Thus, such patients from the Safety/PK assessment period will be included in the OLLI population 2 and DBW population. Also, Safety/PK assessment period and OLLI period may be combined for efficacy/safety analysis with the corresponding population that includes such patients.

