6.18.1. Extent of Exposure

Duration of exposure (in days) to study drug will be summarized by treatment period with corresponding safety population, which is defined in [Table JAHV.6.10](#).

Total PY of exposure will be reported for overall duration of exposure. Descriptive statistics (n, mean, standard deviation [SD], minimum, 1st quartile, median, 3rd quartile and maximum) will be provided for patient-days of exposure, and the frequency of patients falling into different exposure ranges will be summarized. Exposure ranges will generally be reported in weeks using the following as a general guide:

- ≥ 4 weeks, ≥ 16 weeks, ≥ 26 weeks, ≥ 52 weeks

- >0 to <4 weeks, \geq 4 weeks to <16 weeks, \geq 16 weeks to <26 weeks, \geq 26 to <52 weeks, and \geq 52 weeks

Overall exposure will be summarized in total PY which is calculated according to the following formula:

$$PYE = \text{sum of duration of exposure in days (for all patients in treatment group)} / 365.25$$

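### SAP Table JAHV.6.10 ends the general safety population's analysis period at randomization, so the SAP has no throughout-study baricitinib safety summary as planned in protocol 10.3.4, and about 40% of baricitinib patient-years stay unpooled

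*SAP*

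**What the plan says.** Protocol 10.3.4 plans baricitinib summaries in the open-label lead-in (OLLI) period using the OLLI population, and also "throughout the study using general safety population unless otherwise stated".

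SAP 6.1.1 keeps that population broad: "All patients who received at least 1 dose of investigational product, which is baricitinib". It carries no limit on period.

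SAP 6.18, Table JAHV.6.10, then sets the analysis window for this population:

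- Treatment period: "OLLI period and Safety/PK assessment period".
- End of exposure: "date of last dose of baricitinib in safety/PK assessment or OLLI period".
- Events counted: from first baricitinib dose but "before time of randomization in DBW period". Up to 30 days off drug are added only for patients who do not enter the DBW period.

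Baricitinib time after randomization sits in the DBW safety population, by arm. Exposure there runs from randomization to the "date of last dose of treatment in DBW period". SAP 6.1.1 allows the Safety/PK and OLLI periods to be combined, but no column joins open-label and DBW baricitinib time.

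The window carries into the exposure-adjusted incidence rates (EAIRs): "Exposure will be calculated based on the analysis period defined as the treatment period plus up to 30 days off-drug follow-up time". SAP 6.18.1 introduces duration categories with cut-points at 4, 16, 26 and 52 weeks: "Exposure ranges will generally be reported in weeks using the following as a general guide".

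**The concern.** The protocol names a summary that the SAP does not deliver. The population keeps its all-baricitinib definition, but its clock stops at randomization. A child who stays on baricitinib for 44 to 46 weeks appears as 12 to 14 weeks in one column and up to 32 weeks in another, and no table shows the total.

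This matters most for uncommon events such as venous thromboembolism, major cardiovascular events and serious or opportunistic infections. The planned DBW baricitinib arm of 64 is small for a rate of such events, and the open-label column holds no later exposure. The protocol's whole-study summary is where the two would be combined, and the protocol synopsis says that the safety data are meant to inform benefit/risk in nonsystemic JIA.

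**Working it through.** **Inputs.** Protocol 10.1 and SAP 5.2: 197 patients enter OLLI, 65% respond, 128 are randomized 1:1 (64 per arm), flare is 35% on baricitinib and 60% on placebo, DBW dropout is at most 10%. Protocol synopsis: periods of 2, 12 and up to 32 weeks. Protocol 5.1.2: 5 to 8 Safety/PK patients in each of 4 age groups, so 20 to 32. The documents state no patient-year totals, so those below are derived.

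**Plan's own figures.** 128/0.65 = 196.9, so 197. With exponential times, the hazard ratio is ln(0.65)/ln(0.40) = 0.470. With 10% dropout, 57.6 per arm give 57.6 × (0.35 + 0.60) = 54.7 events, and Schoenfeld's formula gives 79.7% power, in line with the stated 80% or so. The exponential reading therefore fits the plan.

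**Open-label exposure.** 197 × 12 × 7/365.25 = 45.3 patient-years (PY). Two extra weeks for 20 to 32 Safety/PK patients add 0.8 to 1.2 PY, giving 46.1 to 46.5 PY.

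**DBW baricitinib exposure.** Combined weekly hazard of leaving: −[ln(0.65) + ln(0.90)]/32 = 0.01675. Mean time on drug: (1 − 0.65 × 0.90)/0.01675 = 24.8 weeks. Total: 64 × 24.8 × 7/365.25 = 30.4 PY.

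**Share outside the general safety column.** 30.4/(30.4 + 46.5) = 39.5%, rising to 40.1% if no Safety/PK weeks are added.

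| DBW assumption | Mean DBW weeks | DBW PY | Share |
|---|---|---|---|
| 50% flare, 10% dropout | 22.0 | 27.0 | 37% |
| 35% flare, 10% dropout | 24.8 | 30.4 | 40% |
| Same, leaving only at 4-weekly visits | 25.6 | 31.4 | 41% |
| 25% flare, 10% dropout | 26.5 | 32.5 | 41% to 42% |
| No flare or dropout | 32.0 | 39.2 | 46% |
| No flare or dropout, mean OLLI time 11 weeks | 32.0 | 39.2 | 48% to 49% |

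**Longest exposure.** The general safety column reaches 12 weeks (direct OLLI entry) or 2 + 12 = 14 weeks (Safety/PK cohort). Continuous baricitinib can reach 12 + 32 = 44 or 14 + 32 = 46 weeks. The categories at 16 weeks and above are therefore empty in that column. The DBW column can fill those at 16 and 26 weeks. Neither column, nor a pooled one, can reach 52.

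**Precision with zero events (3/PY).**

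- Without off-drug follow-up: 3/46.1 = 6.5 per 100 PY as written. Pooled, 3/76.5 to 3/76.9 = 3.9.
- With the full 30 days: the 197 − 128 = 69 non-randomized patients add 69 × 30/365.25 = 5.67 PY, and the 64 DBW baricitinib patients add 5.26 PY. As written, 3/(46.53 + 5.67) = 5.7. Pooled, 3/(76.9 + 5.67 + 5.26) = 3.4. The share becomes (30.4 + 5.26)/87.8 = 41%.

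The true figures lie between, because protocol 5.1.5 requires no follow-up visit from patients who enter the extension study.

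**The case against.** A reader might infer that the SAP narrows the safety population or discards the later baricitinib data. The documents support neither reading.

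- The SAP 6.1.1 definition is intact. Only the analysis period in Table JAHV.6.10 is cut.
- The DBW baricitinib arm has its own exposure, adverse event, laboratory and special-topic summaries against concurrent placebo, which SAP 6.1.4 makes the primary safety analysis.
- SAP 6.18 takes deaths and malignancies to the end of the study and puts all safety data in listings. SAP 6.18.5 lists the cardiovascular and thromboembolic events sent for adjudication. No case disappears.
- Growth is not lost. Table JAHV.6.10 appears to give both columns one baseline, ending before the first baricitinib dose and naming growth explicitly. Change at Week 44 in the DBW baricitinib arm thus spans the whole time on drug.

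The cut may also be deliberate. The protocol sentence ends with an allowance for exceptions, 10.3.4 leaves further detail to the SAP, and the SAP revision history records an update to safety strategy, period and population. The duration categories are described only as a guide, so empty ones are not in themselves an error. Finally, SAP 6.18 places some details in compound-level standards, and the SAP's references cite a program safety analysis plan. Neither is available here, and either could define an all-baricitinib set.

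All of this stands and limits the point to a missing pooled summary in this SAP. It does not remove it: the revision history gives no reason, and protocol 10.3.1 requires a change in analysis methods to be described and justified in the study report.

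**Conclusion.** The point holds as an unexplained departure from protocol 10.3.4. If the SAP is followed as written, a protocol-planned summary is missing, and the broadest baricitinib-only rates come from open-label time alone, with a zero-event bound roughly two-thirds wider than a pooled analysis would give.

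The size rests on planned numbers, on exponential flare and dropout, and on full 12-week OLLI participation. It is unclear whether the 197 include the Safety/PK patients, but this moves the share by less than one percentage point. The statement that nothing pools the periods applies to this SAP only. Primary efficacy and the DBW safety comparison are unaffected, so this should be corrected but does not threaten the trial's main conclusions.

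**What to change.** Add an all-baricitinib column to Table JAHV.6.10. It should run from first to last baricitinib dose across Safety/PK, OLLI and the DBW baricitinib arm, plus up to 30 days off drug, with patients randomized to placebo censored at randomization. Use it for the exposure distribution, for summaries of treatment-emergent events and events of special interest, and for EAIRs. Keep the open-label and DBW columns as they are. The 16- and 26-week categories then become reachable for this population. The 52-week category stays empty and can be dropped or footnoted.

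If the restriction is intended, state the reason in the SAP and carry the justification into the study report, pointing to any other plan that holds the pooled analysis.

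The cost is SAP wording and one extra set of safety tables. No new data are needed.

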6.1.2. Definition of Baseline and Postbaseline Measures

The baseline value for the efficacy (except flare), health outcomes is defined as the last non-missing measurement on or prior to the date of first study baricitinib administration. For patients who participate in the Safety/PK period, this value will be recorded on or before Visit 2 (Day 1); for the other patients who started with the OLLI period, this value will be recorded on or before Visit 5 (Week 0).

The baseline value for disease flare analyses is defined as the last non-missing measurement on or prior to the date of randomization (beginning of the DBW period). This value will be recorded on or before Visit 9 (Week 12).

Baseline for the safety analyses is defined in Section 6.18. Postbaseline measurements are collected after study drug administration through Visit 17 (Week 44) or early discontinuation visit. For data collected in the electronic Clinical Outcomes Assessment (eCOA) tablet (including Patient-Reported Outcomes [PRO] and Clinician-Reported Outcomes [ClinRO]) and related to efficacy assessments, unscheduled postbaseline visits that fall within the visit windows defined by Lilly will be summarized in the by-visit analyses if there is no scheduled visit available. Refer to clinical protocol I4V-MC-JAHV(d) for detail of the visit windows. If there is more than 1 unscheduled visit within the defined visit window and no scheduled visit is available, the unscheduled visit closest to the scheduled visit date will be used. If 2 unscheduled visits of equal distance are available, then the latter of the 2 will be used.

Postbaseline measures for the safety analyses are defined as the nonmissing scheduled (planned) measurements after the date of first study drug administration for continuous measures by-visit analyses and all nonmissing measurements after the date of first study drug administration for all other analyses.

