The primary safety analysis will be conducted during the DBW period for the DBW safety population. Fisher's exact test will be used for the adverse events (AEs), discontinuation, and other categorical safety data for between-treatment group comparisons. Continuous vital signs, body weight, and other continuous safety variables, including laboratory variables will be analyzed by an ANCOVA with treatment group and baseline value in the model. The significance of within-treatment group changes from baseline will be evaluated by testing whether or not the treatment group LSM changes from baseline are different from zero; the standard error and within-group p-value for the LSM change will also be displayed. In addition, the LSM difference between baricitinib and placebo groups, the corresponding p-value, and 95% CI will be provided. Treatment-emergent high/low for categorical laboratory safety analyses will also be produced.

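### Double-blind safety summaries of laboratory, vital-sign and growth measures use a pre-baricitinib baseline, so abnormalities that arose on open-label drug are labelled treatment-emergent on placebo

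*SAP*

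**What the plan says.** SAP Section 6.1.2 does not define the safety baseline itself: "Baseline for the safety analyses is defined in Section 6.18". There, Table JAHV.6.10 has one baseline entry for treatment-emergence and change-from-baseline analyses: "Baseline period: The start of screening and ends prior to the time of first dose of bari administration". For laboratory tests, vital signs and growth, it adds that "baseline will be all scheduled and unscheduled measurements recorded during baseline period".

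The post-baseline row of the same table is split by period. For the DBW period: "The event start time (onset time) is on or after time of randomization in DBW period, up to 30 days off-drug follow-up time". For abnormalities and shifts: "For treatment-emergent abnormal labs, vital signs and shift summaries in labs, all scheduled and unscheduled measurements will be included". Nothing removes or flags a patient whose value was already abnormal at Week 12.

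Proportions are compared with Fisher's exact test. Under SAP Section 6.1.4, continuous measures "will be analyzed by an ANCOVA with treatment group and baseline value in the model"; the same section tests each arm's mean change from baseline against zero.

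Flare is handled differently: "The baseline value for disease flare analyses is defined as the last non-missing measurement on or prior to the date of randomization".

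**The concern.** Everyone who reaches the DBW period has been on baricitinib since Week 0, and the Safety/PK cohort for about two weeks longer. Measured against a pre-drug baseline, a platelet count or lipid level that rose during the open-label period and is still high after randomization appears as a new finding of the DBW period. For a placebo patient, the table then credits placebo with a change that began on study drug.

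The same applies to mean change. A placebo patient's change in height, weight or a laboratory value runs from before the first baricitinib dose, so the test of that change against zero is not a test of what happened on placebo. DBW exposure time is counted from randomization, while treatment-emergence is judged from before the open-label period.

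The ANCOVA also leaves out the Week 12 value, which is closer in time to the outcome and usually more predictive of it. At stake are the reading of the placebo column and the precision of the comparison in the period the SAP names for its primary safety analysis.

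**Working it through.** **1. Plan inputs.** SAP Section 5.2 randomizes 128 patients, 64 per arm. Its power figure concerns flare, not safety, but reproduces. The hazard ratio is ln(0.65)/ln(0.40) = 0.470. Expected events are 64 × 0.35 + 64 × 0.60 = 60.8, or 54.7 after 10% loss, giving 79.7% power by Schoenfeld's formula against a stated figure of about 80%. The point does not rest on it; only the 64 per arm is used below.

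**2. The clocks side by side (Table JAHV.6.10).**
- Baseline: screening to just before the first baricitinib dose.
- DBW post-baseline: from randomization to up to 30 days off drug.
- In between: about 12 to 14 weeks on baricitinib, belonging to neither.

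An adverse event must start on or after randomization, so one that began in the open-label period is not counted. A laboratory or vital-sign abnormality needs only to be present at a DBW measurement and absent at the pre-drug baseline. The hematology tables (SAP 6.18.5.2) follow this: baseline grade is the most extreme in the baseline period, and thrombocytosis is judged from the maximum baseline value.

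**3. Is a Week 12 value available?** The protocol's Table JAHV.2 schedules chemistry, hematology, vital signs, height and weight at Visit 9, and Appendix 2 requires fasting glucose and lipids at Week 12. Some samples may be missing because of blood-volume limits.

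**4. Effect on rates (assumed inputs; the documents give none).** Let c be the share who became abnormal in the open-label period, and pB and pP the shares of these still abnormal at a DBW measurement on baricitinib and placebo. Take new onset after randomization as 20% on baricitinib and 5% on placebo.
- Baricitinib rate = c·pB + (1 − c·pB) × 0.20
- Placebo rate = c·pP + (1 − c·pP) × 0.05
- Difference = 0.15 + c(0.80·pB − 0.95·pP)

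| c | pB | pP | Baricitinib | Placebo | Difference (points) | Fisher power, 64 per arm |
|---|---|---|---|---|---|---|
| 0 | – | – | 20% | 5% | 15 | 67% |
| 0.1 | 1 | 1 | 28% | 14.5% | 13.5 | 38% |
| 0.2 | 1 | 1 | 36% | 24% | 12 | 25% |
| 0.3 | 1 | 1 | 44% | 33.5% | 10.5 | 19% |
| 0.2 | 1 | 0.5 | 36% | 14.5% | 21.5 | 76% |
| 0.3 | 1 | 0.5 | 44% | 19.3% | 24.7 | 82% |

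The placebo rate rises in every carry-over row. The difference does not move one way: with pB = 1 it exceeds 15 points whenever pP < 0.80/0.95 = 0.84.

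**5. Chance imbalance.** Randomization is not stratified on laboratory status. The standard error of the between-arm difference in the share abnormal at Week 12 is √(2c(1 − c)/64): 5.3 points at c = 0.1 and 8.1 at c = 0.3. Tables on the pre-drug baseline cannot show such an imbalance.

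**6. ANCOVA precision (assumed correlations).** With r0 and r12 the correlations of the DBW value with the Week 0 and Week 12 values, replacing Week 0 by Week 12 multiplies residual variance by (1 − r12²)/(1 − r0²).

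| r0 | r12 | Ratio | Variance cut | SE cut |
|---|---|---|---|---|
| 0.5 | 0.6 | 0.64/0.75 = 0.853 | 15% | 8% |
| 0.3 | 0.6 | 0.64/0.91 = 0.703 | 30% | 16% |
| 0.5 | 0.7 | 0.51/0.75 = 0.680 | 32% | 18% |
| 0.3 | 0.7 | 0.51/0.91 = 0.560 | 44% | 25% |

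Keeping both covariates leaves no more residual variance than Week 12 alone, at the price of one degree of freedom.

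**The case against.** The strongest reply is that the pre-drug baseline suits a withdrawal trial. Measured against the untreated state, the tables show abnormalities persisting on continued baricitinib and resolving off it. A Week 12 baseline alone would drop from the baricitinib arm the abnormalities that continued drug maintains, and could hide a drug effect. This stands, and is why the existing tables should stay.

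A reader might infer that the plan biases the comparison or masks a safety signal. The documents do not support that. Carry-over is present in both arms, balanced on average by randomization, and the direction of any change in the difference depends on persistence rates that are not given.

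The flare contrast is also limited. Section 6.1.2 uses the pre-baricitinib baseline for the other efficacy and health outcomes, and flare is by definition worsening from randomization. It shows that a randomization baseline is workable here, not that the safety convention is an anomaly.

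The plan offers partial cover. Open-label safety is summarized separately, box plots show observed values by visit, listings hold all safety data, and Section 6.18 treats safety p-values as flags only. This softens the consequence but leaves the treatment-emergent label and the placebo within-group test as they are. Some details are deferred to compound-level standards not supplied. If the single baseline entry were read as covering only the General Safety Population, the DBW period would have no safety baseline, which would also need correcting.

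**Conclusion.** The point holds for laboratory, vital-sign and growth measures, and not for adverse events. As written, DBW treatment-emergence, shifts and change are judged from before the first baricitinib dose. Abnormalities carried over from open-label treatment are labelled treatment-emergent in both arms, and the placebo within-group change mixes two exposures. The Fisher and ANCOVA comparisons remain valid. The loss is in attribution and interpretation, and usually in precision.

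On size, only the ANCOVA gain has a clear direction: about 15–44% less residual variance (8–25% off the standard error), resting on assumed correlations of 0.3–0.5 for Week 0 and 0.6–0.7 for Week 12. The rates in the working section are illustrations. This is a cheap improvement, not a repair of an invalid analysis.

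**What to change.** - In the DBW safety ANCOVA, include the last value on or before randomization (Visit 9) as a covariate.
- Add a supplementary version of the DBW shift, treatment-emergent and change summaries, including growth, with that value as baseline.
- Keep the pre-baricitinib baseline for the open-label summaries, and keep the existing DBW tables beside the new ones.
- State in Table JAHV.6.10 which baseline applies to each DBW display.

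The cost is SAP wording and extra tables; the data are already scheduled. The new tables show only changes that arise after randomization and omit abnormalities maintained by continued baricitinib, so the two sets must be read together. Where a Visit 9 sample is missing, the covariate falls back to an earlier value.
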